4.4 Scientific rationale for study design

4.5 Justification for dose

The approved monotherapy dose of olaparib is 300 mg twice daily for the tablet formulation (Olaparib IB). However, when used in combination with additional systemic therapies the olaparib dose is often reduced (Olaparib IB). Temozolomide has numerous established dosage regimens pursuant to whether or not it is used in combination with additional systemic agents or radiotherapy (Refer to TMZ package insert). The combination of olaparib and TMZ has been studied in cell line and pre-clinical rodent models. Combination studies in rats suggested potential for olaparib to exacerbate the effects of TMZ, or topotecan, although combination for olaparib with these anticancer agents did not induce any additional target organ toxicities to those seen with single agent administration (Olaparib IB). Furthermore, the olaparib and TMZ combination is actively being investigated in humans in combination with TMZ in both small cell lung cancer and GBM. In GBM PARADIGM-2 is investigating various dose levels up to olaparib 150 mg twice daily (Days 1-5) and TMZ 75 mg/m² daily (continuous) with concomitant radiotherapy (Fulton, Short et al. 2017). Also in GBM the OPARATIC trial concluded continuous TMZ 75 mg/m² and olaparib 150 mg days 1-3 weekly was a safe dose for expansion (Halford, Cruickshank et al. 2017). This further supports the safety of continuous dosing. While in small cell lung cancer a 3+3 dose escalation identified olaparib 200 mg twice daily (Days 1-7) and TMZ 75 mg/m² (Days 1-7) as the recommended phase 2 dose of the combination (Farago, Drapkin et al. 2018). However, to achieve continuous PARP inhibition and PARP trapping, olaparib is being investigated with continuous dosing is being tested by Farago *et al.* At present doses of olaparib 150 mg twice daily (continuous) with TMZ 50-75 mg/m² daily (D1-7) are tolerable with no unanticipated toxicities although published data is unavailable at this time. Therefore, we will proceed with 21 day cycles of olaparib 150 mg twice daily (continuous – days 1-21) + TMZ 75 mg/m² (days 1-7) with a dose de-escalation schema if unacceptable toxicity is observed in the first 6 patients.

4.6 End of study definition

The end of study is defined as the last expected visit/contact of the last patient undergoing the study.

5. STUDY POPULATION

Prospective approval of protocol deviations to recruitment and enrolment criteria, also known as protocol waivers or exemptions, is not permitted.

Each patient should meet all of the inclusion criteria and none of the exclusion criteria for this study in order to be assigned to a study intervention. Under no circumstances can there be exceptions to this rule. Patients who do not meet the entry requirements are screen failures, refer to section 5.4.

 - Total bilirubin $\leq 1.5 \times$ institutional upper limit of normal (ULN)
 - Aspartate aminotransferase (AST) (Serum Glutamic Oxaloacetic Transaminase (SGOT)) / Alanine aminotransferase (ALT) (Serum Glutamic Pyruvate Transaminase (SGPT)) $\leq 2.5 \times$ institutional upper limit of normal unless liver metastases are present in which case they must be ≤ 5 x ULN
 - Patients must have creatinine clearance estimated of ≥ 51 mL/min using the Cockcroft-Gault equation or based on a 24 hour urine test :

$$\text{Estimated creatinine clearance} = \frac{(140 - \text{age [years]}) \times \text{weight (kg)}}{\text{serum creatinine (mg/dL)} \times 72} \times F^a$$

^a where F=0.85 for females and F=1 for males.

10. Eastern Cooperative Oncology Group (ECOG) performance status 0-1 (see Appendix D).
11. Patients must have a life expectancy ≥ 16 weeks.
12. At least one lesion, not previously irradiated, that can be accurately measured at baseline as ≥ 10 mm in the longest diameter (except lymph nodes which must have short axis ≥ 15 mm) with computed tomography (CT) or magnetic resonance imaging (MRI) and which is suitable for accurate repeated measurements.

Reproduction

13. Postmenopausal or evidence of non-childbearing status for women of childbearing potential: negative urine or serum pregnancy test within 28 days of study treatment and confirmed prior to treatment on day 1.

Postmenopausal is defined as:

- Amenorrhoeic for 1 year or more following cessation of exogenous hormonal treatments
- Luteinizing hormone (LH) and Follicle stimulating hormone (FSH) levels in the post menopausal range for women under 50
- radiation-induced oophorectomy with last menses >1 year ago
- chemotherapy-induced menopause with >1 year interval since last menses
- surgical sterilisation (bilateral oophorectomy or hysterectomy)

14. Male patients must use a condom during treatment and for 3 months after the last dose of olaparib when having sexual intercourse with a pregnant woman or with a woman of childbearing potential. Female partners of male patients should also use a highly effective form of contraception ([see appendix C for acceptable methods]) if they are of childbearing potential

5.2 Exclusion criteria

Medical conditions

1. Other malignancy unless curatively treated with no evidence of disease for ≥ 5 years except: adequately treated non-melanoma skin cancer, curatively treated in situ cancer of the cervix, ductal carcinoma in situ (DCIS), Stage 1, grade 1 endometrial carcinoma.
2. Resting ECG indicating uncontrolled, potentially reversible cardiac conditions, as judged by the investigator (eg., unstable ischemia, uncontrolled symptomatic arrhythmia, congestive heart failure, QTcF prolongation >500 ms, electrolyte disturbances, etc.), or patients with congenital long QT syndrome.
3. Persistent toxicities (Common Terminology Criteria for Adverse Event (CTCAE) grade 2) caused by previous cancer therapy, excluding alopecia.
4. Patients with myelodysplastic syndrome/acute myeloid leukaemia or with features suggestive of MDS/AML.

5. Patients with symptomatic uncontrolled brain metastases. A scan to confirm the absence of brain metastases is not required. The patient can receive a stable dose of corticosteroids before and during the study as long as these were started at least 4 weeks prior to treatment. Patients with spinal cord compression unless considered to have received definitive treatment for this and evidence of clinically stable disease for 28 days.
6. Patients considered a poor medical risk due to a serious, uncontrolled medical disorder, non-malignant systemic disease or active, uncontrolled infection. Examples include, but are not limited to, uncontrolled ventricular arrhythmia, recent (within 3 months) myocardial infarction, uncontrolled major seizure disorder, unstable spinal cord compression, superior vena cava syndrome, extensive interstitial bilateral lung disease on High Resolution Computed Tomography (HRCT) scan or any psychiatric disorder that prohibits obtaining informed consent.
7. Patients unable to swallow orally administered medication and patients with gastrointestinal disorders likely to interfere with absorption of the study medication.
8. Immunocompromised patients, e.g., patients who are known to be serologically positive for human immunodeficiency virus (HIV).
9. Patients with known active hepatitis (i.e. Hepatitis B or C).
 - Active hepatitis B virus (HBV) is defined by a known positive HBV surface antigen (HBsAg) result. Patients with a past or resolved HBV infection (defined as the presence of hepatitis B core antibody and absence of HBsAg) are eligible.
 - Patients positive for hepatitis C virus (HCV) antibody are eligible only if polymerase chain reaction is negative for HCV RNA.

Prior/concomitant therapy

10. Any previous treatment with PARP inhibitor, including Olaparib.
11. Any previous treatment with temozolomide or other monofunctional alkylating agent.
12. Patients receiving any systemic chemotherapy or radiotherapy (except for palliative reasons) within 3 weeks prior to study treatment
13. Concomitant use of known strong CYP3A inhibitors (eg. itraconazole, telithromycin, clarithromycin, protease inhibitors boosted with ritonavir or cobicistat, indinavir, saquinavir, nelfinavir, boceprevir, telaprevir) or moderate CYP3A inhibitors (eg. ciprofloxacin, erythromycin, diltiazem, fluconazole, verapamil). The required washout period prior to starting olaparib and temozolomide is 2 weeks.
14. Concomitant use of known strong (eg. phenobarbital, enzalutamide, phenytoin, rifampicin, rifabutin, rifapentine, carbamazepine, nevirapine and St John's Wort) or

moderate CYP3A inducers (eg. bosentan, efavirenz, modafinil). The required washout period prior to starting olaparib and temozolomide is 5 weeks for enzalutamide or phenobarbital and 3 weeks for other agents.

15. Major surgery within 2 weeks of starting study treatment and patients must have recovered from any effects of any major surgery.
16. Previous allogenic bone marrow transplant or double umbilical cord blood transplantation (dUCBT).
17. Whole blood transfusions in the last 120 days prior to entry to the study (packed red blood cells and platelet transfusions are acceptable, for timing refer to inclusion criteria no.8).

Prior/concurrent clinical study experience

18. Participation in another clinical study with an investigational product administered in the last 28 days.
19. Subjects with a known hypersensitivity to temozolomide, olaparib, any of the excipients of either product, or the combination.
20. Patients with a known hypersensitivity to the combination/comparator agent.

Other exclusions

21. Involvement in the planning and/or conduct of the study
22. Judgment by the investigator that the patient should not participate in the study if the patient is unlikely to comply with study procedures, restrictions and requirements.
23. Previous enrolment in the present study.
24. Breast feeding women.

5.3 Lifestyle restrictions

5.3.1 Meals and dietary restrictions

It is prohibited to consume grapefruit juice while on temozolomide and olaparib therapy.

5.3.2 Activity

Contraception

Women of childbearing potential and their partners, who are sexually active, must agree to the use of TWO highly effective forms of contraception in combination (as described in Appendix C). This should be started from the signing of the informed consent and continue throughout the period of taking study treatment and for at least 6 months after last dose of study drug(s), or they must totally/truly abstain from any form of sexual intercourse (as described in Appendix C).

Male patients must use a condom during treatment and for 3 months after the last dose of olaparib when having sexual intercourse with a pregnant woman or with a woman of childbearing potential. Female partners of male patients should also use a highly effective form of contraception (as described in Appendix C) if they are of childbearing potential. Male patients should not donate sperm throughout the period of taking olaparib and for 3 months following the last dose of olaparib.

For details of acceptable methods of contraception refer to Appendix C Acceptable Birth Control Methods.

5.4 Screen failures

Screen failures are defined as patients who signed the informed consent form to participate in the clinical study but are not subsequently entered in the study due to not meeting eligibility criteria. Patients who decide they no longer want to participate in the study either in screening or before completing 1 cycle of therapy will be considered a withdrawal. Minimal information includes demography, screen failure details, eligibility criteria, and any serious adverse event (SAE).

Individuals who do not meet the criteria for participation in this study (screen failure) may be rescreened up to 2 times.

These patients should have the reason for study withdrawal recorded in the eCRF.

6. STUDY TREATMENTS

Study treatment is defined as any investigational product(s) (including marketed product comparator and placebo) or medical device(s) intended to be administered to a study participant according to the study protocol. Study treatment in this study refers to olaparib and temozolamide. If excessive DLTs are observed at the starting doses for the investigational products, alternate doses are outlined in section 4.2.

6.1 Treatments administered

6.1.1 Investigational products

Table 2 **Study Treatments**

	olaparib	Temozolomide
Study treatment name:	Olaparib	Temozolomide
Dosage formulation:	150 mg twice daily	75 mg/m ² days 1-7

Route of administration	Oral	Oral
Dosing instructions:	Olaparib tablets should be taken at the same time each day, approximately 12 hours apart (± 3 hours) with one glass of water. The tablets should be swallowed whole and not chewed, crushed, dissolved or divided. Olaparib tablets can be taken with or without food.	Temozolomide tablets should be taken at the same time as the AM olaparib dose.
Packaging and labelling	Olaparib will be supplied from commercial stock. Study treatment will be provided. Each container will be labelled in accordance with Good Manufacturing Practice (GMP) Annex 13 and per country regulatory requirement.	

If vomiting occurs shortly after the olaparib tablets are swallowed, the dose should only be replaced if all of the intact tablets can be seen and counted. Should any patient enrolled on the study miss a scheduled dose for whatever reason (e.g., as a result of forgetting to take the tablets or vomiting), the patient will be allowed to take the scheduled dose up to a maximum of 2 hours after that scheduled dose time. If greater than 2 hours after the scheduled dose time, the missed dose is not to be taken and the patient should take their allotted dose at the next scheduled time.

6.2 Preparation/handling/storage/accountability

The investigator or designee must confirm appropriate temperature conditions have been maintained during transit for all study treatment received and any discrepancies are reported and resolved before use of the study treatment.

Only patients enrolled in the study may receive study treatment and only authorised site staff may dispense study treatment. At site, all study treatments must be stored in a secure, environmentally controlled, and monitored (manual or automated) area in accordance with the labelled storage conditions with access limited to the investigator and authorised site staff.

The investigator, institution, or the head of the medical institution (where applicable) is responsible for study treatment accountability, reconciliation, and record maintenance (i.e., receipt, reconciliation, and final disposition records).

Further guidance and information for the final disposition of unused study treatment are provided in the pharmacy manual.

6.3 Measures to minimise bias: randomisation and blinding

This is an open-label single arm clinical trial and therefore there is no randomisation or blinding. If a patient withdraws from the study, then his/her enrolment code cannot be reused. Withdrawn patients will not be replaced provided they have completed at least 1 cycle of therapy.

6.4 Treatment compliance

Patients should be given clear instructions on how and when to take their study treatment. Patients will self-administer olaparib and temozolomide. Study site staff will count tablets at regular intervals during treatment. After the tablet count has been performed, the remaining tablets will not be returned to the patient but will be retained by the investigative site. All patients must return their bottle(s) of olaparib and temozolomide at the appropriate scheduled visit, when a new bottle will be dispensed. Patients will be instructed to notify study site personnel of missed doses.

Any change from the dosing schedule, does interruptions, dose reductions, dose discontinuations should be recorded in eCRF.

The Investigational Product Storage Manager is responsible for managing the IMP from receipt by the study site until the destruction or return of all unused IMP. The Investigator(s) is responsible for ensuring that the patient has returned all unused IMP.

6.5 Concomitant therapy

The use of any natural/herbal products or other traditional remedies should be discouraged, but use of these products, as well as any medication or vaccine including over-the-counter or prescription medicines, vitamins, and/or herbal supplements that the patient is receiving at the time of enrolment or receives during the study must be recorded along with:

- Reason for use
- Dates of administration including start and end dates
- Dosage information including dose and frequency

Anti-emetics/Anti-diarrheals

Should a patient develop nausea, vomiting and / or diarrhea, then these symptoms should be reported as AEs (see section 8.3) and appropriate treatment of the event given.

Medications that may NOT be administered

Table 4 **Prohibited medications**

Prohibited medication/class of drug:	
Anticancer therapy:	Not permitted while the patient is receiving study medication
Chemotherapy	
Immunotherapy	
Hormonal therapy*	
Radiotherapy (except palliative)	
Biological therapy	
Other novel agents	
Live virus vaccines	Not permitted while the patient is receiving study medication and during the 30 day follow up period.
Live bacterial vaccines	An increased risk of infection by the administration of live virus and bacterial vaccines has been observed with conventional chemotherapy drugs and the effects with olaparib are unknown.

*Hormone Replacement Therapy (HRT) is acceptable

Restricted concomitant medications

Table 5 **Restricted concomitant medications**

Medication/class of drug:	Usage (including limits for duration permitted and special situations in which it's allowed):
----------------------------------	---

Table 5 **Restricted concomitant medications**

Medication/class of drug:	Usage (including limits for duration permitted and special situations in which it's allowed):
Strong CYP3A inhibitors:	Strong or moderate CYP3A inhibitors should not be taken with olaparib. If there is no suitable alternative concomitant medication then the dose of olaparib should be reduced for the period of concomitant administration. The dose reduction of olaparib should be recorded in the CRF with the reason documented as concomitant CYP3A inhibitor use.
Moderate CYP3A inhibitors:	
 Strong CYP3A inhibitors – reduce the dose of olaparib to 100 mg daily for the duration of concomitant therapy with the strong inhibitor and for 5 half lives afterwards. Moderate CYP3A inhibitors – reduce the dose of olaparib to 100 mg twice daily for the duration of concomitant therapy with the moderate inhibitor and for 3 half lives afterwards. After the washout of the inhibitor is complete, the olaparib dose can be re-escalated.
Strong inducers:	Strong or moderate CYP3A inducers should not be taken with olaparib.
Moderate CYP3A inducers:	
If the use of any strong or moderate CYP3A inducers are considered necessary for the patient's safety and welfare this could diminish the clinical efficacy of olaparib.
 
If a patient requires use of a strong or moderate CYP3A inducer then they must be monitored carefully for any change in efficacy of olaparib and TMZ.

Table 5 **Restricted concomitant medications**

Medication/class of drug:	Usage (including limits for duration permitted and special situations in which it's allowed):

 • CYP3A4 substrates: hormonal contraceptive, simvastatin, cisapride, cyclosporine, ergot alkaloids, fentanyl, pimozide, sirolimus, tacrolimus and quetiapine • CYP2B6 substrates: bupropion, efavirenz • OATP1B1 substrates: bosentan, glibenclamide, repaglinide, statins and valsartan • OCT1, MATE1 and MATE2K substrates: metformin • OCT2 substrates: serum creatinine • OAT3 substrates: furosemide, methotrexate 	
Effect of olaparib on other drugs
 
Based on limited in vitro data, olaparib may increase the exposure to substrates of CYP3A4, OATP1B1, OCT1, OCT2, OAT3, MATE1 and MATE2K.
 
Based on limited in vitro data, olaparib may reduce the exposure to substrates of 2B6.
 
Caution should be observed if substrates of these isoenzymes or transporter proteins are co-administered.

Anticoagulant therapy	Patients who are taking warfarin may participate in this trial; however, it is recommended that international normalised ratio (INR) be monitored carefully at least once per week for the first month, then monthly if the INR is stable. Subcutaneous heparin and low molecular weight heparin are permitted.
Palliative radiotherapy	Palliative radiotherapy may be used for the treatment of pain at the site of bony metastases that were present at baseline, provided the investigator does not feel that these are indicative of clinical disease progression during the study period. Study treatment should be discontinued for a minimum of 3 days before a patient undergoes therapeutic palliative radiation treatment. Study treatment should be restarted within 4 weeks as long as any bone marrow toxicity has recovered.

Table 5 **Restricted concomitant medications**

Medication/class of drug:	Usage (including limits for duration permitted and special situations in which it's allowed):
Administration of other anti-cancer agents	Patients must not receive any other concurrent anti-cancer therapy, including investigational agents, while on study treatment. Patients may continue the use of bisphosphonates or denosumab for bone disease and corticosteroids for the symptomatic control of brain metastases provided the dose is stable before and during the study and they were started at least 4 weeks prior to beginning study treatment.

6.5.1 Background medication

6.5.2 Other concomitant treatment

Other medication other than that described above, which is considered necessary for the patient's safety and wellbeing, may be given at the discretion of the Investigator and recorded in the appropriate sections of the Electronic Case Report Form.

In addition, any unplanned diagnostic, therapeutic or surgical procedure performed during the study period must be recorded in the eCRF.

6.6 Dose Modifications

Dose Reductions

In case a dose reduction is necessary, the Study treatments will be administered as follows:

Table 6 Dose reductions for olaparib to manage adverse events

Initial Dose	Following re-challenge post interruption: Dose reduction 1	Dose reduction 2
150 mg twice daily	100 mg twice daily	100 mg once daily

Table 7 Dose reductions for TMZ to manage adverse events

Initial Dose	Following re-challenge post interruption: Dose reduction 1	Dose reduction 2
75 mg / m ² (days 1-7)	60 mg / m ² (days 1-7)	50 mg / m ² (days 1-7)
*60 mg / m ² (days 1-7)	50 mg / m ² (days 1-7)	40 mg / m ² (days 1-7)
*50 mg / m ² (days 1-7)	40 mg / m ² (days 1-7)	30 mg / m ² (days 1-7)

* If the starting dose of TMZ is lowered as described in section 4.2.

Table 8 Dose reduction for olaparib and TMZ if patient develops moderate renal impairment

Initial Dose	Moderate renal impairment (calculated creatinine clearance by Cockcroft -Gault equation or based on a 24 hour urine test between 31 and 50 ml/min): Dose reduction
Olaparib: 150 mg twice daily	100 mg twice daily
TMZ: 75 mg / m ² (days 1-7)	For TMZ no dose adjustments are required for moderate renal impairment.

For TMZ no dose adjustments are required for renal impairment.

Table 9 Dose reductions for olaparib and TMZ if patient has to start taking a strong or moderate CYP3A inhibitor

Initial Dose	Strong CYP3A inhibitor	Moderate CYP3A inhibitor
Olaparib: 150 mg twice daily	100 mg daily	100 mg twice daily
TMZ: 75 mg / m ² (days 1-7)	For TMZ no dose adjustments are required for concomitant CYP3A4 inhibitors.	For TMZ no dose adjustments are required for concomitant CYP3A4 inhibitors.

For TMZ no adjustments are required for concomitant CYP3A inhibitors.

For guidance on dose reductions for management of AEs (including renal impairment) refer to section 8.4.5.

For guidance on dose reductions when concomitant strong or moderate CYP3A inhibitors cannot be avoided see section 6.5.

When dose reduction for olaparib is necessary patients will take one 100 mg tablet twice (see Section 8.4.5 and Section 6.5).

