
a. An end of treatment visit will be done within 7 days after progression of disease or discontinuation of study treatment for other reasons, and an additional follow up visit at 30 ± 7 days post discontinuation. In the case that the patient initiates a subsequent anti-cancer therapy, the 30 day follow up should occur prior to the first dose of the new therapy and the patient will move to long term follow up.
 
b. After the end of treatment visits the subjects will enter long-term follow up during which information on survival and subsequent anticancer therapy will be obtained by phone every 12 weeks until the subject dies, is lost to follow up, or withdraws consent. Patients who come off study for reasons other than disease progression should be assessed in the clinic and radiographically every 6 weeks (± 7 days) for the first year and 12 weeks (± 7 days) after the first year.
 
c. Vital signs should include temperature, pulse, respiratory rate, weight and blood pressure. Height will be measured on day 1 only. For cycles 2 and beyond, vital signs may be performed up to 2 days before Days 1 and/or 15.
 
d. For treatment cycles 2 and beyond, physical examination, ECOG performance status, weight/BSA may be performed up to 2 days before Days 1 and/or 15.
 
e. Olaparib will be taken continuously at a starting dose of 150 mg twice daily on days 1-21; Temozolomide will be taken days 1-7 every 21 days at a starting dose of 75 mg/m².
 
f. A pregnancy test at screening and on Day 1 is only required for women of “child bearing potential” as defined in the inclusion criteria. If required, the pregnancy test prior to cycle 1 may be done up to 72 hours prior to the treatment of study medications. A pregnancy test is required on day 1 for each cycle (+/- 72 hours) for women of “child bearing potential.”
 
g. For cycle 1 pre-treatment labs should be drawn within 24 hours prior to study treatment. After cycle 1, pre-treatment labs can be drawn up to 72 hours pre-dose.
 
h. TSH (reflex T3, FT4) will be drawn at screening and prior to treatment with cycle 4, and every 4 cycles thereafter (i.e. cycle 8, cycle 12, cycle 16, etc...)
 
i. A baseline CT scan will be done – 28 to -1 days prior to study treatment.
															

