8.4.5 Management of adverse events related to Olaparib and TMZ

Any toxicity observed during the course of the study could be managed by interruption of the dose of the attributed study treatment or dose reductions. Repeat dose interruptions are allowed as required, for a maximum of 4 weeks on each occasion. If the interruption is any longer, the study team must be informed. Olaparib treatment can be dose reduced to 100 mg twice daily. If the reduced dose of 100 mg twice daily is not tolerable, olaparib can be further dose reduced to 100 mg daily, and if this is not tolerable no further dose reduction is allowed and study treatment should be discontinued. Temozolomide can be dose reduced to 60 mg/m² (Days 1-7), and if this is not tolerable TMZ can be further dose reduced to 50 mg/m² (Days 1-7). The following tables should be applied if an AE is deemed to be at least “possibly related” to olaparib, TMZ, or both. If an AE is only attributed to one of the agents the other agent may be continue at an unadjusted dose.

Once dose is reduced, escalation is not permitted (except following concomitant treatment with CYP3A4 inhibitors – see Section 6.5

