8.4.5.3 Renal impairment

If subsequent to study entry and while still on study therapy, a patient's estimated CrCl falls below the threshold for study inclusion (≥ 51 ml/min), retesting should be performed promptly.

A dose reduction is recommended for patients who develop moderate renal impairment (calculated creatinine clearance by Cockcroft-Gault equation or based on a 24 hour urine test of between 31 and 50 ml/min) for any reason during the course of the study: the dose of olaparib should be reduced to 100 mg twice daily.

No dose reductions for TMZ are required for moderate to severe renal impairment, although caution is advised in cases of CrCl < 36 ml/min. Because the CrCl determination is only an estimate of renal function, in instances where the CrCl falls to between 31 and 50 mL/min, the investigator should use his or her discretion in determining whether a dose change or discontinuation of therapy is warranted.

Olaparib has not been studied in patients with severe renal impairment (creatinine clearance ≤ 30 ml/min) or end-stage renal disease; if patients develop severe impairment or end stage disease it is recommended that study treatment be discontinued.

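### Section 6.6 closes with a single olaparib reduction instruction that, read as twice daily, is double the daily dose the protocol sets for a strong CYP3A inhibitor and for the second adverse-event step

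*Combined protocol and SAP*

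**What the plan says.** The starting dose is set in the notes to the Schedule of Activities: "Olaparib will be taken continuously at a starting dose of 150 mg twice daily on days 1-21".

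Reductions are then described in several places.

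- **Section 6.6, closing sentence:** "When dose reduction for olaparib is necessary patients will take one 100 mg tablet twice". It carries no condition and no time unit, and it refers to Sections 8.4.5 and 6.5.
- **Section 6.5, Table 5, strong CYP3A inhibitor:** "reduce the dose of olaparib to 100 mg daily for the duration of concomitant therapy with the strong inhibitor". Table 9 in Section 6.6 gives the same dose.
- **Section 6.5, Table 5, moderate CYP3A inhibitor:** "reduce the dose of olaparib to 100 mg twice daily for the duration of concomitant therapy with the moderate inhibitor". Table 9 agrees.
- **Section 6.6, Table 6, adverse events:** first 100 mg twice daily, then "100 mg once daily". Tables 11, 12 and 13 repeat these two steps.
- **Section 8.4.5, second adverse-event step:** "olaparib can be further dose reduced to 100 mg daily, and if this is not tolerable no further dose reduction is allowed".
- **Section 8.4.5.3, moderate renal impairment:** "the dose of olaparib should be reduced to 100 mg twice daily". Table 8 agrees. The same section also leaves the decision on a dose change or discontinuation to the investigator's discretion.
- **Section 8.4.5, on going back up:** "Once dose is reduced, escalation is not permitted", with an exception for the period after CYP3A4 inhibitor treatment.

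**The concern.** The closing sentence reads as a general dispensing rule, yet each of the two sections it cites contains a reduction that does not fit it. Section 6.5 has the strong-inhibitor dose, and Section 8.4.5 has the second adverse-event step. These are patients for whom the protocol asks for the larger reduction: those taking the stronger class of interacting drug, and those who did not tolerate the first reduced dose.

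Two things are at stake. The first is patient safety, because patients take the tablets themselves (Section 6.4) and depend on one clear instruction. The second is compliance and reporting. Section 8.4.3 treats a dose or frequency above the protocol regimen as an overdose to be reported, and for an AstraZeneca study drug the company must be told within 24 hours. A strong-inhibitor patient taking 200 mg/day would comply with the closing sentence and exceed Tables 5 and 9. The protocol does not settle whether that is an overdose.

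**Working it through.** There is no statistical figure to reproduce. The check sets the passages side by side and converts each to a daily dose.

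Formula: daily dose = mg per dose × doses per day.

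Inputs:
- Starting dose (Schedule of Activities notes): 150 × 2 = 300 mg/day.
- Closing sentence of Section 6.6: one 100 mg tablet, with *twice* read as twice daily: 100 × 2 = 200 mg/day.

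| Situation | Where the dose is set | Daily dose there | Share of starting dose | Closing sentence ÷ that dose |
|---|---|---|---|---|
| Adverse events, step 1 | Table 6; Section 8.4.5; Tables 11–13 | 100 × 2 = 200 mg | 200/300 = 67% | 200/200 = 1.0 |
| Adverse events, step 2 | Table 6; Section 8.4.5; Tables 11–13 | 100 × 1 = 100 mg | 100/300 = 33% | 200/100 = 2.0 |
| Strong CYP3A inhibitor | Tables 5 and 9 | 100 × 1 = 100 mg | 100/300 = 33% | 200/100 = 2.0 |
| Moderate CYP3A inhibitor | Tables 5 and 9 | 100 × 2 = 200 mg | 200/300 = 67% | 200/200 = 1.0 |
| Moderate renal impairment | Table 8; Section 8.4.5.3 | 100 × 2 = 200 mg | 200/300 = 67% | 200/200 = 1.0 |

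The sentence agrees with the tables in three situations and gives double the daily dose in two. At step 2 it would leave the patient on the 200 mg/day of step 1, so there would be no second reduction.

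**Secondary check: patients already reduced.** Tables 8 and 9 have one olaparib row each, for an initial dose of 150 mg twice daily. Table 5 and Section 8.4.5.3 give fixed doses. Table 6, however, creates patients at 200 and 100 mg/day.

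| Current dose | Strong inhibitor (100 mg/day) | Moderate inhibitor or moderate renal impairment (200 mg/day) |
|---|---|---|
| 200 mg/day (step 1) | lower than current | equal to current |
| 100 mg/day (step 2) | equal to current | higher than current; barred by the no-escalation sentence in Section 8.4.5 |

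In three of these four cells the fixed dose gives no reduction from the current dose. The documents do not say what then applies, beyond the investigator's discretion in the renal case.

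**The case against.** **The sentence is a loose summary that defers to the detailed rules.** It lacks a time unit, it points to Sections 8.4.5 and 6.5, the text just above it sends readers to Section 6.5 for inhibitors, and Table 9 is on the same page of rules. The strong-inhibitor dose is the same in both places that set it. The second adverse-event step is the same in Table 6, Section 8.4.5, Section 8.4.5.2 and Tables 11 to 13. A careful pharmacist would probably find the specific row. This stands as a reason to think an error less likely. It does not remove the contradiction, because the sentence is unconditional and no text gives the tables precedence.

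**A reader might infer that the protocol prescribes a dose increase** for a patient at 100 mg once daily who starts a moderate inhibitor or develops moderate renal impairment. The documents do not support that. Section 8.4.5 bars escalation after a reduction, and its exception covers only the time after inhibitor treatment. Tables 8 and 9 are headed by the initial dose and do not claim to cover patients already reduced, and the renal rule leaves room for discretion. What remains is a gap in coverage.

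**A reader might also infer that the dose-limiting toxicity (DLT) count or the rate of grade 3 or higher adverse events is distorted.** That is not shown. Exclusion criterion 13 bars strong and moderate inhibitors at entry with a 2-week washout, and Table 5 allows them on study only when no suitable alternative exists. DLTs count only in cycle 1 of the safety cohort, and events with a clear alternative explanation are set aside. The documents give no frequency of inhibitor use from which an effect could be estimated.

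**Conclusion.** The contradiction is real. For a strong CYP3A inhibitor and for the second adverse-event step, the closing sentence of Section 6.6 and the tables differ by a factor of two, 200 against 100 mg/day. In the other three situations they agree.

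The factor of two rests on one assumption, that *twice* means twice daily. This is the natural reading. Without it the sentence states no daily dose at all and still needs correcting.

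It would go too far to say that patients would receive twice the intended dose, since the documents do not say which text expresses the intention. The supportable statement is that two operative instructions conflict and a site cannot tell which one is compliant or when the overdose rule is triggered. The handling of patients already on a reduced dose is a secondary clarification. The primary endpoint, sample size and error rates are not affected.

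**What to change.** Reconcile the closing sentence of Section 6.6 with Tables 5, 6 and 9 and Section 8.4.5, so that each situation has one stated dose with a time unit. If the sponsor confirms the tables, the sentence can be deleted or replaced by a reference to the table row that applies. If the sponsor intends something else, the tables and Section 8.4.5 must change to match. The sponsor decides the doses; this review takes no position on them.

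In the same amendment, clarify how the fixed doses in Tables 5, 8 and 9 relate to the reduced levels in Table 6 and to the no-escalation sentence in Section 8.4.5 when the current dose is not 150 mg twice daily.

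The cost is a wording correction in Sections 6.5, 6.6 and 8.4.5, including 8.4.5.3, in the next amendment. Sample size and timelines do not change.
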